7.8 Visit 5 Follow- Up (Day 168±5)

At Visit 5, the following will take place:

- Record concomitant medications
- Physical examination, including weight
- Vital signs (SBP, DBP, HR)
- Plasma concentration sample collection
- GGT, ALT, AST, and total bilirubin
- Bone Turnover Markers
- Fasting Lipid Profile
- Coagulation
- 12-lead ECG
- DXA Scan
- Grip Strength and SPPB (to be performed before the PADLs/IADLs and SF-36)
- Post-fracture PADLs/IADLs
- SF-36
- 6MWT and BORG Scale (to be performed after the PADLs/IADLs and SF-36)
- Record adverse events

8 DATA MANAGEMENT

8.1 Data Collection

All data (ECGs, clinical laboratory data, and all other study-related data) will be collected according to the CRO's SOPs.

8.2 Database Management and Quality Control

Data items from the eCRFs are entered into the study database. Subsequently, Data Management staff, using both electronic and manual checks, systematically checks the data. Obvious errors (self-evident corrections) will be corrected and documented by Integrium personnel. Other errors or omissions will result in queries, which will be sent electronically to the investigational site.

Concomitant medications entered into the database will be coded using the World Health Organization (WHO) Drug Reference List, which employs the Anatomical Therapeutic Chemical classification system. Coexistent diseases and adverse events will be coded using the most recent Medical dictionary for regulatory activities (MedDRA) terminology.

Clinical laboratory samples will be processed by ACM Global Central Laboratory at [name], and the results will be sent electronically to Integrium. For plasma concentration samples, MicroConstants, Inc., [name], will determine the drug concentration at both time points and the information will be submitted electronically to Integrium. Both clinical laboratory and plasma concentration results are imported into the database.

8.3 Quality Assurance and Database Lock

A 100% critical variable review of all key safety and efficacy data in the database will be performed. Following this review, a data quality control audit equal to the square root plus 1 of the total population will be performed.

A random sample equal to the square root plus 1 of the total population will be sampled for a quality assurance audit prior to database lock.

When the database has been declared to be complete and accurate, the database will be locked. Any changes to the database after that time can only be made by joint written agreement between the Sponsor, Integrium and the study biostatistician.

9 STATISTICAL METHODS

9.1 Justification of Sample Size

Based on the observed change in total lean body mass information from previous studies (as percentage change in total lean body mass information is not available), it seems reasonable to estimate the placebo-adjusted difference in total lean body mass for the 0.5 mg group to be 0.5 kg and 1.0 kg for the 1 mg group. For the purpose of power calculations, the 2 mg group is extrapolated to show a 1.5 kg adjusted difference. The estimate of standard deviation, based on information from the previous study, is estimated to be 1.3. A sample size of 30 subjects per treatment group yields 84% power to detect a

difference between the 1 mg treatment group and placebo and 99% power to detect a difference between the 2 mg treatment group and placebo.

Even though the sample size estimate is based on the observed change in total lean body mass, we believe that the resulting calculations are reasonable for the analysis of percentage change in body less head lean body mass.

9.2 Definition of Populations

All subjects who have taken a single dose of the study drug and provide follow-up information will be included in the safety population.

All subjects who have taken a single dose of the study drug and have a valid pre-baseline and post-baseline efficacy assessment will be included in the Intent-to-Treat population.

All subjects who have taken at least 80% of the expected number of doses and do not have a major protocol violation will be included in the Per Protocol population.

9.3 Efficacy Analysis

9.3.1 DXA Scan Measurements

The total body less head and total lean body mass, hip bone mineral density, total body weight and fat mass, appendicular lean body mass and bone turnover markers will be analyzed using an Analysis of Covariance model with baseline value as a covariate and treatment as a primary factor.

Observed values, percentage change and absolute change from baseline and placebo adjusted change from baseline will be summarized using mean, standard deviation, coefficient of variation (CV%), median, minimum and maximum. A 95% confidence interval on the placebo adjusted change from baseline will also be presented.

9.3.2 Physical Performance Assessments

The 6MWT total distance walked will be analyzed using an Analysis of Covariance model with baseline value as a covariate and treatment as a primary factor. Observed values, change from baseline and placebo adjusted change from baseline will be summarized using mean, standard deviation, coefficient of variation (CV%), median, minimum and maximum.

Grip strength will be analyzed using an Analysis of Covariance model with baseline value as a covariate and treatment as a primary factor. Observed values, change from baseline and placebo adjusted change from baseline will be summarized using mean, standard deviation, coefficient of variation (CV%), median, minimum and maximum.

SPPB score will be summarized using frequency counts. Observed values and change from baseline will be summarized. A Kruskal-Wallis test (ANOVA on ranks) will be used to test for differences between treatment groups.

9.3.3 Patient Reported Outcomes

The SF-36 individual subscales (Physical Functioning (PF), Role-Physical (RP), Bodily Pain (BP), General Health (GH), Vitality (VT), Social Functioning (SF), Role-Emotional (RE) and Mental

Health (MH)) and summary measures (Physical Health and Mental Health) will be analyzed using an Analysis of Covariance model with baseline value as a covariate and treatment as a primary factor. Observed values, change from baseline and placebo adjusted change from baseline will be summarized using mean, standard deviation, median, minimum and maximum.

The PADLs/IADLs will be analyzed as follows:

- Change in number of subjects entirely dependent in performing each activity of daily living from screening at each post-screening visit will be analyzed using the Cochran-Mantel-Haenszel Test.
- Difference in number of subjects entirely dependent in performing each activity of daily living at each visit between treatment groups will be compared using the Cochran-Mantel-Haenszel Test.
- Each activity of daily living for each visit collected will be summarized using mean, standard deviation, median, minimum and maximum.
- Significant change from screening for each activity of daily living will be analyzed using the Wilcoxon signed-rank test.
- Differences between treatment groups for each activity of daily living will be analyzed using the Kruskal-Wallis test on the change from screening value.

9.4 Plasma Concentrations Analysis

Pre-dose and single post-dose plasma concentrations at Visits 2 and 4 will be summarized using mean, standard deviation, coefficient of variation (CV%), median, minimum and maximum.

Correlations between T_{max} and trough plasma concentrations and total lean body mass (observed and change from baseline) will be derived and presented in a graphical layout.

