3.2 Secondary Objective(s)

The secondary objectives of this study are:

- To assess the safety and tolerability of VK5211 after 12 weeks of treatment by comparing overall adverse events, vital signs, 12-lead ECG data, physical examinations, and hematology/chemistry/urinalysis data to placebo.
- To determine the efficacy of VK5211 after 12 weeks of treatment by mean placebo-corrected change in:
 - Hip bone mineral density (BMD) assessed by DXA
 - Total lean body mass
 - Appendicular lean body mass
 - Bone turnover markers (s-CTX and s-PINP)
- To assess plasma concentration of VK5211 near T_{max} and at trough levels in relation to total lean body mass.

The exploratory objectives of this study are to determine the efficacy of VK5211 compared to placebo after 12 weeks of treatment by:

- Physical Performance Assessments
 - 6MWT and BORG Scale
 - Grip Strength
 - SPPB
- Patient Reported Outcomes
 - Pre- and Post-fracture PADLs/IADLs
 - SF-36

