6.10 DXA Scans

DXA scans will be performed at Randomization and at Visits 4 and 5, or in case of early withdrawal as shown in [Table 1](#). Instructions for DXA scans are provided in the study reference manual.

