6.12 Plasma Concentration Sample Collection

Blood samples to determine plasma study drug concentration will be collected at Visits 2, 3, 4 and 5 as shown in [Table 1](#).

Pre-dose samples will be collected on the appropriate days at 0 to 20 min pre-dose (Visits 2, 3, and 4). A single post-dose sample will be collected thereafter at 2 hours (\pm 10 min) post-dose (Visits 2, 3, and 4), plus one additional sample at Visit 5.

At each collection, 5 mL of blood will be collected into a Vacutainer tube containing lithium heparin (green top) and immediately placed in an ice bath. Within 30 minutes of collection, the plasma fraction will be separated by centrifugation at 2,500 rpm (1,000 x g) for 15 minutes at 4°C. The plasma fraction will be separated into equal aliquots and transferred into 2 labeled 5 mL polypropylene tubes and frozen at approximately -20°C or -70°C.

Blood volume collected for these samples will be approximately 20 mL total per subject.

Plasma concentration samples should be shipped on dry ice via overnight delivery to MicroConstants for analysis. Samples will ship only on a Monday, Tuesday or Wednesday to minimize the possibility of the samples being in transit over a weekend. Duplicate plasma concentration samples will ship after MicroConstants confirms receipt of the initial samples.

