The subject must have a valid baseline DXA and a DXA after baseline and prior to 98 days after starting treatment.

For the lean body mass measurements, the number and percent of subjects who had a 0.5kg, 1.0kg, 1.5kg and 2.0kg increase from baseline will be presented, and the number and percent of subjects who increased by 3% and number and percent of subjects who increased by 5% will also be presented.

Correlations and regression lines between total lean body mass (for both observed values and change from baseline) and the VK5211 PK concentration near Tmax and at trough levels will also be analyzed for each VK5211 treatment group and all VK5211 treatment groups combined. This analysis will be performed by visit and for all post-baseline visits combined.

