2.10.2.2. Plasma Concentration Analysis

Pre-dose and single post-dose plasma concentrations of VK5211 at Visits 2, 3 and 4 and the single plasma concentration at Visit 5 will be summarized using mean, geometric mean, standard deviation, coefficient of variation (CV%), median, minimum and maximum.

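### Concentration-lean mass analysis: the pairing of samples with scans is undefined, and a same-visit pairing rests the on-drug exposure-response on one Visit 4 sample and stacks off-drug Visit 5 pairs

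*Protocol*

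**What the plan says.** Protocol 3.2 makes it a secondary objective to assess VK5211 concentration near Tmax and "at trough levels in relation to total lean body mass". Protocol 9.4 supplies the method in one sentence, which covers near-Tmax values too: correlations for "trough plasma concentrations and total lean body mass (observed and change from baseline) will be derived and presented in a graphical layout". It names no visit pairing and no exposure measure.

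SAP 2.10.2.1 adds regression lines, to be run "for each VK5211 treatment group and all VK5211 treatment groups combined", and then: "This analysis will be performed by visit and for all post-baseline visits combined".

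The two measurement schedules differ:

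- Protocol 6.12: "Blood samples to determine plasma study drug concentration will be collected at Visits 2, 3, 4 and 5". Samples are pre-dose and 2 hours post-dose at Visits 2, 3 and 4, with one sample at Visit 5.
- Protocol 6.10: "DXA scans will be performed at Randomization and at Visits 4 and 5, or in case of early withdrawal". Protocol 2.9 excludes plasma sampling at early termination.

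SAP 2.10.2.2 gives the concentrations a descriptive summary: "Pre-dose and single post-dose plasma concentrations of VK5211 at Visits 2, 3 and 4 and the single plasma concentration at Visit 5". Neither document defines an averaged or cumulative exposure.

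**The concern.** A 12-week change in lean mass reflects 12 weeks of exposure. If each Month 3 scan is matched only with the Visit 4 sample, exposure is represented by one trough, or one 2-hour value, near the end of treatment. That value carries occasion-to-occasion variation from adherence, dose timing and assay error. Under classical measurement error, such variation in the explanatory variable biases the slope and the correlation toward zero. A real relationship within a dose group could look weak or absent although earlier samples that would reduce the noise are already in the database.

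The combined analysis raises a separate problem. The only other scheduled same-visit pair is Visit 5, at Day 168 against an end of treatment near Day 84, when concentrations are presumably near zero. Stacking those pairs mixes exposure-response with persistence of effect after the drug is stopped.

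**Working it through.** **Which pairs exist** (Protocol Table 1, 2.9, 6.10, 6.12)

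| Visit | Plasma | DXA | Same-visit pair |
|---|---|---|---|
| 2 | pre-dose, 2 h | none | none |
| 3 | pre-dose, 2 h | none | none |
| 4 | pre-dose, 2 h | yes | on drug |
| 5 | one sample | yes | about 12 weeks off drug |
| Early termination | none | yes | none |

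The carry-forward rule in SAP 2.16 fills only Months 3 and 6, so it creates no lean mass value at Visit 2 or 3.

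**Plan's own figure.** There is none for this analysis: no power, no reliability, no concentration CV. The one design power statement (30 per group, SD 1.3 kg) reproduces at 84.6% for 1.0 kg and 99.4% for 1.5 kg, taking two-sided alpha as 0.05, but does not bear on this point.

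**Attenuation model.** Let B = ln(1 + between-subject CV²), W = ln(1 + within-subject CV²), and k = number of visits averaged on the log scale. Reliability is λ = B / (B + W/k). The observed slope is the true slope × λ, and the observed correlation is the true r × √λ. DXA error lowers r further but does not bias the slope.

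Assumed, because the documents give nothing: between-subject CV 30-60%, within-subject CV 20-50%.

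*Within one dose group*

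- Least favourable (30%, 50%): B = 0.0862, W = 0.2231. λ = 0.0862/0.3093 = 0.28 for k = 1, 0.44 for k = 2, 0.54 for k = 3.
- Middle (40%, 30%): B = 0.1484, W = 0.0862. λ = 0.1484/0.2346 = 0.63, then 0.77 and 0.84. The factors on r are 0.80, 0.88 and 0.92.
- Most favourable (60%, 20%): B = 0.3075, W = 0.0392. λ = 0.3075/0.3467 = 0.89, then 0.94 and 0.96.

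With about 23 completers per group (SAP 2.14) and a true r of 0.50, Fisher z power in the middle case is 47%, 56% and 60% for one, two and three visits.

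*All doses pooled, without dose adjustment, as the SAP plans*

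With dose-proportional exposure, B gains the variance of ln(0.5, 1, 2) = (2/3)(ln 2)² = 0.320.

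- Least favourable: λ = 0.4065/0.6296 = 0.65, then 0.79 and 0.85.
- Middle: λ = 0.4687/0.5549 = 0.84, then 0.92 and 0.94.
- Most favourable: λ = 0.6278/0.6670 = 0.94, then 0.97 and 0.98.

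Power at a true r of 0.30 with 3 × 23 = 69 subjects:

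| Case | One visit | Two visits | Three visits |
|---|---|---|---|
| Least favourable | 51.5% | 59.9% | 63.3% |
| Most favourable | 68.3% | 69.6% | 70.1% |

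Three visits gain about 2-12 points and two visits about 1-8.

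The SAP does not state the scale. On raw concentrations the middle-case pooled slope factor, by simulation, is 0.79 with one visit and 0.92 with three.

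**Stacking Visit 5.** Illustrative simulation: true slope 0.8, residual SD 1.3, CVs 40% and 30%, Visit 5 concentration set to zero.

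| Analysis | Slope | r |
|---|---|---|
| Visit 4 only | 0.63 | 0.40 |
| Stacked, gain fully kept at Visit 5 | 0.35 | 0.21 |
| Stacked, half kept | 0.53 | 0.33 |
| Stacked, none kept | 0.70 | 0.42 |

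The stacked result depends heavily on how long the effect persists, which is not the question posed by the secondary objective.

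**The case against.** The strongest reply is that no rule in the documents restricts the Month 3 scan to Visit 4 samples. Protocol 9.4 is silent, and the SAP's by-visit wording could mean each visit's concentration against the Month 3 change. This stands: the exclusion of Visits 2 and 3 is an inference from the natural reading. The silence is itself a gap, since the programmer must choose.

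A reader might also infer that the scan and sample fall on the same day. They need not: the stringent definition in SAP 2.10.2.1 allows a scan up to 14 days after treatment stops, and the liberal one any scan after baseline and before day 98. Nor are the earlier samples unused altogether, since SAP 2.10.2.2 summarises them.

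The protocol also limits timing noise. Visits 2 and 4 are fasting, at about 8 am, with the dose given in clinic, narrow sampling windows and a three-day diary beforehand. That supports the lower end of the assumed within-subject CV, but does not remove assay error or variation in adherence between visits.

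Finally, power is a weak yardstick for an analysis with no stated hypothesis test, and in the middle case a single group of 23 stays underpowered even with three visits. Both points are fair. Bias in the estimated slope remains whether or not anything is tested.

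**Conclusion.** The concern holds in limited form. The pairing is unspecified, no averaged exposure is defined, and the natural reading gives a single-sample exposure for the Month 3 response plus a combined analysis contaminated by off-drug pairs. The direction of the bias is secure under classical error. Its size is not, because every reliability figure rests on assumed CVs.

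On those assumptions one visit understates the within-dose slope by 11-72%, and the pooled slope by about 6-35%, where the four-fold dose range protects the analysis. Averaging recovers part of this, not all. A reader might infer a large, quantified loss of power for the secondary objective; the documents do not support that, and the pooled gain is modest. The primary endpoint is unaffected. The change is worth making because it uses data already collected.

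**What to change.** In SAP 2.10.2.1 and Protocol 9.4:

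1. Define each VK5211 subject's exposure as the mean log trough and, separately, the mean log 2-hour concentration over on-treatment Visits 2 and 4. Add Visit 3 only where timing against the last dose is confirmed.
2. State how values below the limit of quantification are handled, since the log needs a rule.
3. Relate these exposures to the Month 3 change in total lean body mass, by dose group and pooled.
4. Keep the Visit 4-only pairing as supportive.
5. Analyse Visit 5 separately and drop it from the combined analysis.

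The Visit 3 text must be reconciled first. Table 1 footnote 9 and Protocol 6.12 schedule pre- and post-dose samples there, but footnote 11 lists no administration. Protocol 9.4 summarises only Visits 2 and 4, while the SAP includes Visit 3. The stated total of about 20 mL matches four 5 mL samples, whereas the schedule has seven (35 mL).

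Cost: the added SAP and protocol wording, one derived exposure variable for each sample type, and slightly more analysis. No new sample, visit or patient is needed.

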9.5 Safety Evaluation

All safety variables (including adverse experiences, vital signs measurements, clinical laboratory results, ECG results, and other safety variables) will be listed by subject and domain. The incidence of all AEs, treatment-emergent adverse experiences, and treatment-related adverse experiences will be tabulated by MedDRA® preferred term, system organ class, dose, and treatment group. All laboratory results, vital sign measurements, and other safety variables will be summarized using appropriate descriptive statistics. The incidence of treatment emergent abnormalities will be summarized by dose.

9.5.1 Adverse Events

Adverse events (AE) will be coded using the most current version of MedDRA and tabulated, including categorical information of interest such as onset and resolution times, time of onset relative to dose, severity at onset, causal relationship to study medication, and action taken. AEs will be regarded as 'pretreatment' if they occur between Screening and the time of administration of the first dose of VK5211 and will be recorded as medical history.

Treatment-emergent adverse events (TEAEs) are defined as any AE that started after the first dose of study medication or started prior to the first dose but increased in severity or frequency after dosing. The incidence of TEAEs will be presented by system organ class and preferred term. Adverse events will also be summarized by severity and relationship to the study drug. The incidence of AEs leading to withdrawal from the study will be presented.

Listings of any serious adverse events (SAEs), deaths, and AEs or abnormal laboratory values leading to discontinuation of a subject from the study will be presented.

9.5.2 Laboratory Evaluations

Individual laboratory values will be listed by visit and summarized using descriptive statistics. Individual change from baseline in laboratory values will be calculated and summarized descriptively. Shift tables from baseline to final visit will also be produced for the laboratory assessments based on the categories of Low, Normal, and High. A clinically significant change from baseline may be recorded as an AE if deemed appropriate by the PI or sponsor.

9.5.3 Vital Signs

Individual vital sign measurements (systolic/diastolic BP and heart rate) will be listed by measurement time and summarized using descriptive statistics. Individual change from baseline in vital sign measurements will be calculated and summarized descriptively. A clinically significant change from baseline may be recorded as an AE if deemed appropriate by the PI or sponsor.

9.5.4 Physical Examination and ECG

Physical examination results and ECG results will be summarized for each visit at which they are performed. Any clinically significant change from baseline may be recorded as an AE if deemed appropriate by the PI or sponsor. Individual ECG values will be listed by visit and summarized using descriptive statistics. Intervals to be provided for each ECG are: RR, PR, QRS, QT, and QTcF.

9.5.5 Concomitant Medications

Prior and concomitant medications will be identified using the most current version of the WHO Drug dictionary. The incidence of prior and concomitant medications will be summarized.

9.6 Handling of Missing, Unused, or Spurious Data

Descriptive statistics and listings will be provided for all data. No substitution of missing data will be used in any calculations. Data points that appear to be spurious will be investigated and will not be excluded from the listings. Influential cases will be handled in an appropriate statistical manner.

10 ADVERSE EVENTS AND SAFETY REPORTING

10.1 Safety Assessments

Safety will be assessed on an ongoing basis by adverse events, identification of dose-limiting toxicities (DLTs), (if any), general physical examinations, vital signs, clinical laboratory assessments in blood and urine according to the Common Terminology Criteria for Adverse Events (CTCAE)

version 4.03 [http://evs.nci.nih.gov/ftp1/CTCAE/CTCAE_4.03_2010-06-14_QuickReference_8.5x11.pdf].

Clinical safety data will be reviewed by the medical monitor on an ongoing basis. Safety data will undergo formal review by an independent Data Monitoring Committee (DMC) who will meet on a regular basis and ad hoc as needed, will receive unblinded data results, and will make recommendations on continuation of the study.

